5.1 Schedule of events

	Screening (Visit 0)	Baseline (Visit 1)	Pre-HT (Visit 2)	Post-HT/RT (Visit 3)	6 weeks post HT/RT (Visit 4)	12 weeks post HT/RT (Visit 5)	Disease progression (Visit 6)	10 baseline (Visit 7)	10 – 3wks (Visit 8)	10-6wks (Visit 9)	10-disease progression (Visit 10)	12 months post HT/RT
Eligibility criteria	X											
Participant information	X											
Informed consent		X										
Medical record monitoring		X	X	X	X	X	X	X	X	X	X	X
EORTC QLQ-C30		X		X	X	X						
EORTC QLQ H&N35		X		X	X	X						
Sample collection: blood		X	X*	X	X	X	X	X	X	X	X	
Sample collection: saliva		X	X*	X	X	X	X	X	X	X	X	

*This may be omitted if baseline measures were collected. Omission may occur due to logistical issues (i.e., difficult to arrange with the participant)

Abbreviations: HT, hyperthermia; IO, Immunotherapy; RT, radiotherapy.

- **Treatment visits**

This is an interventional study to implement superficial hyperthermia in the real-world setting, and the patients will continue their clinical visits and follow-up as per normal standard of care. We will obtain the treatment outcome from medical records of patients. It will be during patients' SOC visits that we will collect biological samples and assess PROMs. All patients will be assessed using the European Organization for Research and Treatment of Cancer (EORTC) Quality of Life Core Questionnaire (QLQ-C30). Additionally, the HNSCC cohort will also be assessed using the European Organisation for Research and Treatment of Cancer Quality of Life Questionnaire Head and Neck Module. PROM assessments will take place during the same timepoints as biological sample collection, with the last PROM assessment taking place at 12 weeks post radiotherapy.

8. Subject selection

We will have the following cohorts of patients undergoing standard of care treatments, which we plan to include 15 to 20 patients in each disease cohort* and up to 60 patients in total:

1. HNSCC cohorts

- i. Inoperable/recurrent HNSCC with no previous radiotherapy treatment
- ii. Inoperable/recurrent HNSCC with previous radiotherapy treatment (re-irradiation)

2. cSCC cohort

- i. Inoperable/recurrent cSCC with no previous radiotherapy treatment
- ii. Inoperable/recurrent cSCC with previous radiotherapy treatment (re-irradiation)

3. LRBC cohorts

- i. Inoperable locally recurrent breast cancer with previous radiotherapy treatment (re-irradiation)

* The number of participants may vary between each group

- **Subject inclusion criteria**

1. Patient with histologically confirmed incurable or recurrent cancers with disease [at least one superficial lesion(s) or lymph node(s)] suitable for hydrosun® TWH1500 treatment
2. Patient suitable for SOC palliative radiotherapy or re-irradiation with one of the pre-specified palliative radiotherapy dose and fractionation (Table 1 above)
3. Aged ≥18 years old
4. Eastern Cooperative Oncology Group (ECOG) performance status 0 to 2
5. Capacity to consent

- **Subject exclusion criteria**

1. No superficial tumour lesion or lymph node that is suitable for hydrosun® TWH1500 treatment
2. Patients are not suitable for one of the pre-specified palliative radiotherapy dose and fractionation (table 1 above)
3. Has known psychiatric or substance abuse disorders that would interfere with cooperation with the requirements of the study

- **Collection of biological samples for translational research**

We propose to develop a detailed investigation of total immune profile of patients following palliative radiotherapy +/- superficial hyperthermia to tumour lesion(s). Some of these patients may subsequently undergo palliative anti-PD1 or anti-PDL1 checkpoint antibody as part of the standard treatments. Understanding the immune responses to various treatments will help us to stratify and optimize patients' treatments and to combine different treatment modalities in a personalized manner. We also aim to uncover prognostic and predictive biomarker that could help to deliver a more personalized treatment in cancer patients undergoing palliative radiotherapy with superficial hyperthermia who may or may not subsequent anti-PD1 antibody as part of the standard of care.

We will assess peripheral immune responses as well as free and vesicular Hsp70 in the bloods from patients undergoing treatment at baseline and post-treatments:

- 1) palliative radiotherapy (RT) + hyperthermia: baseline, pre-hyperthermia treatment, post-hyperthermia/radiotherapy treatment (post-third or fourth fraction of RT), 6 weeks (+/- 2 weeks) post hyperthermia/radiotherapy, 12 weeks (+/- 2 weeks) post hyperthermia/radiotherapy and at the first disease progression post hyperthermia/radiotherapy.
- 2) For patients who will subsequently undergo anti-PD1/PD-L1 checkpoint inhibitor: baseline immunotherapy, 3 weeks (+/- 2 week) post-baseline immunotherapy, 6 weeks (+/- 2 weeks) post-baseline immunotherapy and at the first disease progression post immunotherapy. We will obtain whole blood and isolate PBMC from patients' blood and high parameter immune profile will be investigated with CyTOF (Mass Cytometry). In addition, we will assess free and vesicular serum and plasma Hsp70 from the patients, which will be correlated with the Hsp70 expression in tumour tissues and tumour infiltrating CD561 NK cells in formalin-fixed paraffin embedded (FFPE) tumour specimens (24-25). We will also assess immune markers on the diagnostic paraffin-embedded tissues (pre-treatment + post-treatment or post-recurrence if available) from the same cohort of patients. The peripheral immune responses will be correlated with the results done on tumour immune markers using Imaging Mass Cytometry. We will process additional blood samples according to the SOP

provided by [name] for parallel biomarker work on liquid immune profile-based signature (LIPS) (26). In addition, blood samples will be collected for other translational research including assessment of ctDNA at the above time points. We will aim to collect blood samples at the same time that the patients are having blood tests at GSTT as part of the standard procedures or occasionally as an additional procedure in the time points above. On each occasion, we will take up to 40ml of blood. We may also ask them to donate other samples such as saliva, oral swab, urine or faeces for future research at the same time points above. The blood samples and any available fresh samples collected will be transported from Guy's Hospital (by foot) to [name] laboratory at Guy's site at KCL. Translational research may be conducted for up to 5 years after the recruitment period.

9. Study procedures

- **Subject recruitment**

- **Method of recruitment**

All eligible candidates will be identified and screened for eligibility criteria from the relevant tumour multidisciplinary team (MDT) and/or oncology clinics, and the initial approach to the potential participants will be made by the direct care team members. All cases will be discussed with the lead hyperthermia consultant ([name]) or designated clinical sub-investigator prior to consent to the study. Participating patients should aim to start treatment as per usual standard of care.

- **Payment**

The participants will not be paid for this study since patients will not be required to have additional visits other than their standard of care visit.

- **Informed consent**

This study will initially be opened at Guy's and St Thomas' NHS foundation trust. Additional centres (including those in the overseas) may be opened later after appropriate ethical approval and funding is obtained in the respective country and centre. The Principal Investigator (PI) retains overall responsibility for the conduct of research at participating site with delegation of duties to appropriate clinical sub-investigators (e.g., clinical fellow), which includes the taking of informed consent of participants at their site with the processes below:

- Checking the inclusion and exclusion criteria
- A discussion with the potential participant about the research including the nature and objectives of this study and possible risks associated with their participation

- Patient information leaflet and consent form will be given to patients, usually at least 24 hours before consent
- Potential participants will be given the opportunity to ask questions
- Assessment of the mental capacity for the participants to consent will be performed by either the PI or the appropriate clinical sub-investigators. The PI will ensure that any person delegated the responsibility to participate in the informed consent process is duly authorised, trained and competent to participate according to the ethically approved protocol, principles of Good Clinical Practice (GCP) and Declaration of Helsinki.

To promote equitable representation and improve the generalizability of study findings, this research is committed to including non-English speaking participants. The consent process for the ThermoRad wIRA study is conducted independently from the standard radiotherapy consent process at Guy's Hospital. In accordance with institutional policy, all non-English speaking participants must be consented for radiotherapy in the presence of a GSTT-licensed interpreter. To ensure accurate understanding during the ThermoRad wIRA consent process, we will endeavour to implement one of the following procedures:

1. Pre-consent translation and telephone interpretation: A family member will be present in person to assist with translating the pre-consent discussion. During the formal consent process, a GSTT-qualified interpreter will be contacted via telephone to ensure the participant comprehends all study-related information. Both the participant and the accompanying family member will sign the consent form, and the name of the telephone interpreter will be recorded by the consenting clinician on the form.
2. Reinforcement during radiotherapy consent: During the radiotherapy consent appointment, the GSTT-licensed interpreter present will be asked to review the ThermoRad wIRA consent information with the participant to confirm understanding of the study and consent previously obtained.

▪ **Translational research**

Participants will be asked to give generic consent for their samples, derived organoids and/or cell lines and linked data to be transferred and used in future research. This includes the transfer and use of samples/data to KCL and its partners including the commercial sector and overseas organisations. Based on this consent, archival tissue, blood, saliva, oral swab, urine and stool samples will be collected and stored at Guy's and St Thomas' head and neck biobank during the study; and will be

stored beyond the ethical approval date of the project and stored under the custodial of [name] (HTA licence 12121; Licence Holder [name]) if the patients sign an additional biobank consent. All material will be handled in accordance with the Human Tissue Act 2004 and other relevant legislation relating to the use of cell lines. Specific agreements will be put in place as required by the Sponsor including material transfer agreements where necessary.

- **Withdrawal of consent**

The right of a patient to refuse participation without giving reasons will be respected. The patient will remain free to withdraw at any time from the trial without giving reasons and without prejudicing his/her further treatment and will be provided with a contact point where he/she may obtain further information about the trial. Patients will be made aware of the terms and conditions around withdrawal. If a patient withdraws from the study, the research team can retain any biological samples and DNA/RNA samples up until the time of the patient's withdrawal if the patient agrees. Any unused samples taken for research purpose can be destroyed if patients request to do so. Any demographic and medical information already provided or results from tests already performed on their samples will continue to be used in the study, however no further data or sample collection will be performed. If a patient consents to the study but subsequently lose the capacity to consent during the study, he/she will be withdrawn from the study. However, we will retain and make further use of any identifiable data and collected tissues. We can destroy any unused samples taken for research purpose upon the request from the patient or the next of kin. We will also stop taking any further blood or other samples from the patient although we would like to continue collecting follow-up information from the hospital record and/or GP in regard to patients' disease status and survival outcome.

- **Screening Procedures**

No extra screening investigations are needed for this study since this is a real-world implementation study. Patients will undergo routine standard of care investigations and treatments apart from consenting to this study and for their samples to be used for translational research during their routine standard of care procedures

- **Schedule of assessments for each visit**

Patients will undergo assessments as per normal standard of care and the schedule will not be changed due to this study.

- **Follow-up procedures**

The follow-up procedures will be as per normal standard of care and the schedule will not be changed due to this study. We will obtain relevant clinical information from the medical records.

- **End of Study Definition**

The patient recruitment for the prospective study will initially be 24 months from the commencement of the study at coordinating site, Guy's and St. Thomas' NHS Foundation trust. Thereafter, the patients will be followed up for their long-term treatment outcome and survival as per normal standard of care. We will continue to obtain relevant information on patients' treatment and survival outcome from patients' medical records. The end of the study definition is 12 months from the last participant recruited into the study. We will assess whether the endpoints and outcomes are met at the end of the study, particularly the real-world implementation of superficial hyperthermia (using CE marked water-filtered infrared A (wIRA) machine) in addition to palliative radiotherapy and whether we are able to recruit the target number of patients.

We will submit the protocol for a major amendment towards the end of the study if the study is to continue for up to an additional 3 years of recruitment, providing further funding is obtained. Otherwise, we will analyse all data and produce the final study report at the end of third year.

The criteria for progression beyond the two-year recruitment period are set as below:

1. The study recruits well and reaches the target number of patients (up to 60 patients)
2. The study showed that superficial hyperthermia with wIRA could be implemented in the real-world setting and used in combination with palliative radiotherapy in cancer patients
3. Further funding is obtained to continue beyond the two-year recruitment period

10. Laboratories

Collected patients' samples from Guy's Hospital as part of translational research will be transferred to [name] laboratory at Kings College London for further processing. The samples will be pseudo-anonymised with sample IDs which can be linked to patients. The sample processing will be done by the research assistant appointed for the study and/or [name] lab members and only those with KHP passport will have access to patients' confidential information. The samples will not be transferred or given to anyone without an MTA agreement. However, if there are any successfully generated organoids from any fresh samples, the anonymised organoids may be shared with collaborators. Based on the consent from patients, any other unused blood, saliva, oral swab, urine, and stool samples will be stored at Guy's and St Thomas' head and neck biobank beyond the ethics approval date of the project.

These samples can only be transferred or used if there is an MTA agreement in place. The samples will be stored for up to 5 years under the custodial of [name] (HTA licence 12121; Licence Holder [name]) for future analysis and possible future research. If the samples are not used by then, they will be destroyed according to the standard operating procedure of the biobank. Further details on the sample collection, processing, storage, and analysis will be provided in the laboratory manual.

- **Data Recording/Reporting**

All staff that would directly deal with human tissues or blood will undertake HTA training.

- **Sample Receipt/Chain of Custody/Accountability**

Handling of the samples upon arrival at the laboratory needs to be documented. Upon receipt of the samples, the laboratory should ensure that the physical integrity of these samples have not been compromised in transit. If it has, it is important that the study teams, as well as the sponsor, are informed of this. Upon receipt of samples laboratory staff should ensure that all samples are accounted as per the labeling. All samples received should be logged in an accountability log.

- **Sample transfer to sites outside the organization**

Individual informed consent will be obtained from the patients to specify whether they would agree for their samples to be transferred to collaborating third parties including overseas and commercial laboratories on behalf of KCL. This may include but not be limited to validation of research results.

The patient samples and derived organoids (with linked data) may be shared with collaborating laboratories, nationally or internationally, for the purposes of facilitating the research aims. Specific agreements will be put in place as required by the Sponsor including material transfer agreements where necessary. Any commercialisation of the results of this study will be specified in contractual arrangements between parties where necessary and participants will be informed that they would not benefit financially.

11. Assessment of Safety

This is a real-world implementation study, and the patients participated in this study will undergo superficial hyperthermia in addition to SOC palliative radiotherapy. Hyperthermia treatment has not shown to significantly increase acute or late toxicities compared to radiotherapy alone. In a summary of the clinical outcomes of 38 clinical trials across various tumour sites using hyperthermia did not report any significant increase in reported acute or late toxicity with the addition of hyperthermia (19). Similarly, in a systematic review of the use of hyperthermia in addition to radiotherapy for head and neck cancer (20), did not report any worsening toxicities from the addition of hyperthermia, apart

from one study reporting a 30% increase of thermal blisters however both older radiotherapy and hyperthermia techniques have been used (22). The Hydrosun system has been evaluated in superficial breast cancer re-irradiation with no acute grade 2-4 toxicities been observed, including no burning with blistering (18). We will collect safety profile data from the patients undergoing superficial hyperthermia with SOC palliative radiotherapy in this study.

- **Procedures for Recording and Reporting Adverse Events**

No serious adverse events (SAEs) are expected to occur due to hyperthermia alone, but it can sensitize radiotherapy. For patients undergoing palliative radiotherapy and hyperthermia, they will be followed up by their treating clinicians as per normal practice.

The HRA gives the following definitions for Safety Reporting (Research other than Clinical Trials of Investigational Medical Products (CTIMPs)) for UK Health Departments' Research Ethics Service (RES):

Serious Adverse Event (SAE) is defined as an untoward occurrence that:

- a) Results in death; or
- b) Is life-threatening; or
- c) Requires hospitalization or prolongation of existing hospitalization or
- d) Results in persistent or significant disability or incapacity; or
- e) Consists of a congenital abnormality or birth defect; or
- f) Is otherwise considered medically significant by the investigator.

In line with the study sponsor conditions and HRA guidance, if a SAE is discovered and thought to be related to superficial hyperthermia (+/- SOC palliative radiotherapy), the CI will immediately report upon knowledge of the event to the R&D Department within 24 hours. If the SAE is considered to be related to superficial hyperthermia (+/- SOC palliative radiotherapy) and unexpected, it will also be reported to the relevant REC committee within 15 days of the CI becoming aware of the event. The HRA defines SAEs as related to the study if it involves the administration of any of the research procedures and unexpected as in that it was not listed in the protocol as an expected occurrence. If the CI deems a SAE to be disease-related and not related to the superficial hyperthermia (+/- SOC palliative radiotherapy), the SAE will be documented but only reported in the final study report. Therefore, only SAEs that are localised to the site of hyperthermia (local adverse events) will be reported. Participants will be monitored for SAEs for 6 weeks after completion of radiotherapy. All documentation relating to SAEs will be kept in the Trial Master File.

12. Compliance and withdrawal

- **Subject compliance**

We will monitor the percentage of approached participants who consent to taking part in the study during the first year of recruitment.

- **Withdrawal/dropout of subjects**

We will monitor the percentage of participants who withdraw consent or drop out from the study after taking part. We will replace the subjects if necessary to make up the total target number of patients (n=30) as long as this is within the recruitment period.

- **Protocol compliance**

The patients will undergo routine treatments as per standard of care.

13. Data

- **Data management**

As this is a real-world implementation study, we will collect data from patients that are already available in the hospital record on patients' demographics, smoking and alcohol history, tumour characteristics including HPV status when applicable, proposed treatment plans. The patients' treatment details, treatment responses, progression and survivals will also be obtained from clinical record. They will be recorded on paper CRFs. Participant files and paper CRFs will be identified using a Participant Identification Number. Personal information will not be stored on CRFs. Screening and enrolment logs will be maintained by the research team. For enrolled participants, identifiable patient data will be stored in an Excel file for the purposes of gathering follow-up data. This file will be password protected and stored on the KCL secured network, whereby access is only granted by the PI to named individuals.

Paper CRFs, consent forms and the Trial Master File will be stored in locked filing cabinets within the [name] (KCL, [name]). Data generated from laboratory processes related to the generation of PDOs and subsequent testing will be kept in the research laboratory. These data will be identified with the PIN and no personal data will be used in the lab records.

- **Data linkage**

If the participating patients have come from or will move to different health care providers, we will attempt to get either available archival tissues and/or data from the relevant health care providers

after sending them the relevant patients' consent forms. We may also go to the central national databases with a patient's NHS number to get clinical data if necessary.

14. Statistical considerations and additional participating sites

This is a prospective study to assess the implementation of wIRA superficial hyperthermia machine in the real-world setting and no formal power calculation is performed. The number of patients chosen for each cohort is the expected number of patients that we anticipate recruiting within 24 months based on the number of cancer patients that we treat at Guy's Cancer Centre. The study will initially commence as a single-site study at GSTT. Other UK sites may be added via a substantial amendment in due course if they acquire the same CE marked machine and would like to participate in the study. Consideration as to whether sites outside of the UK will be able to take part in the study will be considered in due course although this may not be possible due to the different health policy and the additional ethical approval requirement. The data from this prospective study will be used to calculate the sample size required if we extend the study beyond two years of recruitment or to plan a future interventional study, which will be submitted as a major amendment.

15. Ethical considerations

- **Research Ethics Committee (REC) review & reports**

Before the start of the trial, approval will be sought from an NHS REC for the trial protocol, informed consent forms, patient information sheet, and GP information letters.

Any amendments to the protocol or study documents will be reviewed by the Sponsor, sent to the REC for review and approvals. No changes will be implemented until approval has been received from the REC and approved by the Trust R&D department, if required.

All correspondence with the REC will be retained in the Trial Master File.

An annual progress report (APR) will be submitted to the REC within 30 days of the anniversary date on which the favourable opinion was given, and annually until the trial is declared ended. The Chief Investigator's will approve the annual report which will be submitted by the CI or delegate.

The CI will notify the REC of the end of the trial within 90 days of the end of the study. If the trial is ended prematurely, the CI will notify the REC, including the reasons for the premature termination.

Within one year after the end of the trial, the Chief Investigator will submit a final report with the results, including any publications/abstracts, to the REC.

- **Peer review**

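### Withdrawal ends record-based follow-up with no option to keep it, although record follow-up is sought after loss of capacity and SAE monitoring excepts no one who withdraws

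*Protocol*

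**What the plan says.** Section 9, Withdrawal of consent, sets the rule for a patient who withdraws from the study: information and test results already held "will continue to be used in the study, however no further data or sample collection will be performed". A choice is described for biological material only. Samples may be retained if the patient agrees, and "Any unused samples taken for research purpose can be destroyed if patients request to do so". No choice is described for future information from records.

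The same paragraph then covers patients who "subsequently lose the capacity to consent during the study, he/she will be withdrawn from the study". For them sampling stops, but "we would like to continue collecting follow-up information from the hospital record and/or GP", limited to disease status and survival.

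Section 9, End of Study Definition, states the general source of outcomes: "We will continue to obtain relevant information on patients' treatment and survival outcome" from medical records. Treatment visits (under Schedule of events), Follow-up procedures (Section 9) and Data management (Section 13) likewise describe outcomes as taken from routine records.

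Section 11 states: "Participants will be monitored for SAEs for 6 weeks after completion of radiotherapy". No exception is made for patients who withdraw. Section 12 adds: "We will monitor the percentage of participants who withdraw consent or drop out from the study after taking part". It also allows such patients to be replaced.

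Under the Synopsis and Table 1, patients without an event are censored at the last date on which they were known to be event-free.

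**The concern.** In this study outcomes are read from the hospital record at routine visits. A patient who wants no more study procedures may have no objection to the team continuing to read that record. The protocol nevertheless ends that collection for anyone who withdraws, and does not provide for asking whether they would allow it. The loss is therefore partly self-imposed.

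The terms also pull against each other. A patient able to decide is not offered record follow-up, while it is sought for one who can no longer decide, and both are called withdrawn. The SAE commitment in Section 11 cannot be met for someone who withdraws before the six-week window closes.

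At stake are local SAEs and response (when withdrawal comes before they are recorded), and PFS, OS and local control (when withdrawal is related to the patient's course). Section 14 says that the data will be used to size an extension or a later study, so any distortion would carry forward. An analysis plan cannot repair this, because it cannot recover data that the protocol says will not be collected.

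**Working it through.** The protocol states no withdrawal rate, power or target precision, so there is no figure to reproduce. The check has two parts.

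**1. The rules side by side**

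| Situation | Rule on future record data | Where |
|---|---|---|
| Patient withdraws from the study | None collected; past data kept | Section 9, Withdrawal of consent |
| Patient withdrawn after losing capacity | Disease status and survival wanted, worded as a wish; safety not named | Section 9, same paragraph |
| Patient stops hyperthermia, samples or questionnaires but does not withdraw | Not addressed; general record follow-up applies on a plain reading | Section 9, Follow-up procedures and End of Study Definition |
| SAE monitoring | To six weeks after radiotherapy, no exception stated | Section 11 |

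The first two rows give one label two different data rules. The first and fourth rows cannot both be followed for a patient who withdraws during treatment or within six weeks after it. The third row is left to each reader.

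**2. How much could be lost (illustration)**

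Cohort size (15 to 20) and total (up to 60) come from Section 8. Withdrawal rates, event counts and median survival are assumptions.

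*Proportions.* With N patients, w withdrawn with unknown outcome and x events among the N − w observed, the full-cohort proportion lies between x/N and (x + w)/N.

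- N = 60, w = 6 (10%). SAE: observed 5/54 = 9.3%; range 5/60 = 8.3% to 11/60 = 18.3%. Response: observed 30/54 = 55.6%; range 30/60 = 50.0% to 36/60 = 60.0%.
- N = 60, w = 12 (20%). SAE: observed 5/48 = 10.4%; range 5/60 = 8.3% to 17/60 = 28.3%. Response: observed 26/48 = 54.2%; range 26/60 = 43.3% to 38/60 = 63.3%.
- Within one cohort, each unknown outcome is worth 1/20 = 5.0 to 1/15 = 6.7 percentage points. That is a feature of the cohort size, not of this rule.

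*Survival.* True 12-month survival with exponential times is exp(−12 × ln 2 / median): 35.4% for a median of 8 months and 50.0% for 12 months. Kaplan-Meier estimates were simulated with 200,000 patients under two patterns: withdrawal unrelated to outcome, and withdrawal one month before death among patients dying within 12 months.

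| Median (true 12-month survival) | Withdrawn | Unrelated | One month before death |
|---|---|---|---|
| 8 months (35.4%) | 5% | 35.3% | 38.0% |
| 8 months (35.4%) | 10% | 35.3% | 41.1% |
| 8 months (35.4%) | 20% | 35.5% | 48.1% |
| 12 months (50.0%) | 5% | 50.0% | 53.5% |
| 12 months (50.0%) | 10% | 50.0% | 57.2% |
| 12 months (50.0%) | 20% | 50.0% | 65.4% |

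Unrelated withdrawal leaves the estimate essentially unbiased. The upward shift appears only when withdrawal is tied to outcome, and the second pattern is deliberately strong.

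**The case against.** The strongest reply is that the rule governs patients who withdraw from the study, and nothing defines stopping hyperthermia, refusing blood tests or skipping a questionnaire as withdrawal. Sampling is already flexible, and record follow-up does not depend on finishing treatment. On that reading a patient who stops heat because it is intolerable and later has a local SAE is still captured. This stands, and it limits the point to patients who actually withdraw.

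A reader might infer that the likeliest treatment failures leave the safety and survival endpoints. The documents do not support that:

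- They give no withdrawal rate and no link between withdrawal and outcome.
- Patients who lose capacity, plausibly a deteriorating group, are the ones the protocol hopes to keep following.
- Data up to withdrawal stay in use and event-free patients are censored, so they are not removed from the survival analyses.
- Only withdrawal before the SAE window closes affects SAE capture.
- Withdrawals are counted under Section 12, so they are not lost as information about implementation.

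It can also be argued that the two groups differ for good reason, since one patient chose to leave and the other did not, and that the SAE sentence is a general rule with withdrawal as its implied exception. Both readings are possible. Neither explains why a patient who withdraws is given no choice about records, and the SAE exception is not written down.

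Finally, the consent pages are not available for review and may offer more options. They could not override an explicit protocol rule that collection stops.

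**Conclusion.** The point holds in limited form. As written, the protocol gives up record-based SAE, response, progression and survival data that a withdrawing patient might willingly allow. It also uses one label for two data rules, and its SAE commitment does not fit its withdrawal rule.

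The consequence is avoidable missing data and a risk of informative censoring, not demonstrated bias. Its size is unknown: the figures above rest on assumed withdrawal rates, event counts and medians, and the survival shift also on an assumed tie between withdrawal and death. Replacement of withdrawn patients could add to any selection, but that too depends on who withdraws. The change is worth making because it is cheap and the lost data cannot be recovered later.

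**What to change.** Amend Section 9 and the consent wording as follows:

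1. State that stopping hyperthermia, samples or questionnaires is not withdrawal from the study, and that record follow-up then continues.
2. Offer a patient who withdraws an explicit choice to allow continued collection from medical records. Only an explicit refusal ends it, so the right to refuse all further collection is preserved.
3. Record the level chosen on the CRF, with its date.
4. Use the same terms for loss of capacity, with record follow-up as approved by the REC, and say whether it includes safety data.
5. Reconcile the SAE sentence in Section 11 so that it covers everyone who has not refused record collection.

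The cost is a protocol amendment with REC review, revised consent wording, one CRF field, and re-consent of participants already enrolled. No extra visits are needed, because the outcomes already come from routine records.
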